7.5 SECONDARY ENDPOINTS

7.5.1 Key secondary endpoints

Key secondary endpoints will be analyzed in a hierarchical manner to preserve the Type I error. If the test for the primary endpoint is successful, then testing will continue for the first

key secondary endpoint of time to ischemic stroke with two-sided $\alpha=0.05$. If this test is statistically significant, then the second key secondary endpoint of time to non-fatal stroke, non-fatal MI, and cardiovascular death will be tested with two-sided $\alpha=0.05$. If at any point, the null hypotheses for the primary or key secondary endpoints cannot be rejected, formal testing will stop.

Key secondary endpoints will be analyzed using the same Cox proportional hazards regression model (with covariates) as the primary endpoint. All secondary analyses as determined by the adjudication committee will be performed on the RS for the full follow-up period.

No multiplicity adjustments are planned for other secondary endpoints. Nominal p-values will be reported for descriptive purposes.

7.5.2 (Other) Secondary endpoints

Other secondary endpoints will be analyzed using the same Cox proportional hazards regression model (with covariates) as the primary endpoint. All secondary analyses will be performed on the RS for the full follow-up period.

No multiplicity adjustments are planned for other secondary endpoints. Nominal p-values will be reported for descriptive purposes.

7.7 EXTENT OF EXPOSURE

Extent of exposure to trial medication within the study will be displayed by treatment to the extent that data were collected for the TS. Both descriptive statistics and categorization by exposure intervals (e.g., cumulative exposure intervals <1, 1 - <3, 3 - <6, 6 - <12, 12 - <18, 18 - < 24, 24 - < 30, 30 - < 36 months, >36 months, if applicable) will be used.

Extent of observation time (defined as: date of randomization to date of last contact) will be summarized similarly. The same intervals will be used except for combining the first three intervals into 0-6 months.

7.8 SAFETY ANALYSIS

All safety analyses will be performed on the treated set as randomized.

The primary safety endpoint is time to first major bleed.

Secondary safety endpoints are:

- Time to first intracranial hemorrhage
- Time to life-threatening bleed
- Time to fatal bleed
- Time to first bleed (all severities)

Further safety endpoints are:

Only investigator-determined major and potentially major bleeds are adjudicated. Bleeding endpoints (as determined by the adjudication committee) that will be analyzed are: major bleeds, intracranial hemorrhage, life-threatening and fatal bleeds.

Time to event endpoints will be analyzed using the same Cox proportional hazards regression model as the primary endpoint. No multiplicity adjustments are planned for safety endpoints.

7.8.1 Adverse events

Analyses of adverse events will be descriptive in nature. All analyses of AEs will be based on the number of patients with AEs and NOT on the number of AEs.

Furthermore, for analysis of AE attributes such as duration, severity, etc. multiple AE occurrence data on the CRF, will be collapsed into AE episodes provided that all of the following applies:

- The same MedDRA lowest level term was reported for the occurrences
- The occurrences were time-overlapping or time-adjacent (time-adjacency of 2 occurrences is given if the second occurrence started on the same day or on the day after the end of the first occurrence)
- Treatment did not change between the onset of the occurrences OR treatment changed between the onset of the occurrences, but no deterioration was observed for the later occurrence

For further details on summarization of AE data, please refer to the guideline 'Handling and summarization of adverse event data for clinical trial reports and integrated summaries' [5].

The analysis of adverse events will be based on the concept of treatment emergent adverse events. That means that all adverse events occurring between first drug intake until 6 days after last drug intake will be assigned to the randomized treatment. All adverse events occurring before first drug intake will be assigned to ‘screening’ and all adverse events occurring after last drug intake + 6 days will be assigned to ‘post-treatment’ (for listings only). For details on the treatment definition, see [Section 6.1](#). In general, adverse events attributed to ‘Screening’ or ‘Post-treatment’ will be listed only.

An overall summary of adverse events will be presented.

Frequencies [N (%)] of patients with adverse events will be summarised by treatment, primary system organ class and preferred term (using MedDRA). Separate tables will be provided for patients with serious adverse events.

The system organ classes will be sorted according to the standard sort order specified by EMA, preferred terms will be sorted by frequency (within system organ class).

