6. INVESTIGATIONAL PLAN

6.1 VISIT SCHEDULE

Informed consent of all study patients will be obtained in compliance with ICH and GCP guidelines and the principles stipulated in the Declaration of Helsinki prior to any study related procedure.

The study will consist of three sequential periods, a Screening period of up to 14 days, a Treatment Period of approximately 6-36 months and a Follow up Period of one month. The maximum treatment duration is expected to be 36 months, however, the trial can conclude earlier, if adequate number of events are reported sooner. It can conclude later (or enroll additional patients) if more time is needed to observe the minimum number of required events.

The schedule for trial visits is summarised in the study [Flow Chart](#) including time windows for study visits. All visit dates are calculated from the date of randomisation. In the event that visits are missed or out of sequence, subsequent visits will be planned according to the date of randomisation.

No protocol waivers will be given (e.g. Sponsor will not grant permission to include a known ineligible patient). In the case of medical emergencies, prior approval from the Sponsor for protocol deviations (e.g. visit schedule) will not be required, but BI should be notified as soon as possible. The relevance of any such protocol deviation will be assessed prior to analysing the data.

The procedures to be conducted at each visit are provided in the Flow Chart and further described below.

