7.3.3 Safety analyses

Analysis of all bleeding endpoints (as listed in [Section 5.2.1](#)) will be performed on the TS population for the on-treatment period. The pre-specified bleeding endpoints will also be analyzed using the RS set as a sensitivity analysis and for publication purposes.

Time to event endpoints will be analyzed using the same Cox proportional hazards regression model as the primary endpoint. No multiplicity adjustments are planned for safety endpoints. Minor bleeds and CRNMBE will be presented using descriptive statistics.

Adverse events will be analyzed from the TS population. AEs recorded prior to first intake of trial medication will be assigned to 'screening'. The REP is 6 days (refer to [Section 5.2.2.2](#)). All adverse events with an onset after the first dose of study medication up to a period of 6 days after the last dose of study medication will be assigned to the on-treatment period for evaluation. Those after the REP, but prior to the last per protocol contact will be assigned to 'post treatment', and those after the last per protocol contact will be assigned to 'post-study'. The same applies for planned measurements (e.g. vital signs or laboratory parameters) with the exception that measurements between start and last per protocol contact will be assigned to the corresponding treatment. These assignments including the corresponding time intervals will be defined in detail in the TSAP.

Adverse events will be coded using the Medical Dictionary for Regulatory Activities (MedDRA) coding dictionary. Standard BI summary tables and listings will be produced to compare the incidence of adverse events.

Laboratory data will be analyzed both quantitatively as well as qualitatively. The latter will be done via comparison of laboratory data to their reference ranges. Values outside the reference range as well as values defined as clinically relevant will be highlighted in the

listings. Treatment groups will be compared descriptively. Even if randomization occurred based on local lab, Visit 1 results of the central laboratory analyses will be used for the analyses.

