7. PLANNED ANALYSIS

For End-Of-Text (EoT) tables, the set of summary statistics is: N / Mean / SD / Min / Median / Max.

For tables that are provided for endpoints with some extreme data, median, quartiles and percentiles should be preferred to mean, standard deviation, minimum and maximum.

Tabulations of frequencies for categorical data will include all possible categories and will display the number of observations in a category as well as the percentage (%) relative to the respective treatment group (unless otherwise specified, all patients in the respective patient set whether they have non-missing values or not). Percentages will be rounded to one decimal place. The category missing will be displayed only if there are actually missing values.

When composite endpoints are evaluated as survival endpoints, the time to first onset date of any of the events listed in the composite endpoint will be used as the date of the event. For combined endpoints of non-fatal and fatal events, the time to the first event is taken. If the fatality is the first event, then the time to death (not the time to the event leading to death) is taken. For example, if a patient has a stroke at study day 100 and subsequently dies due to stroke (as adjudicated) on day 110. For the combined endpoint “Non-fatal stroke, non-fatal MI, CV death” the day of event would be day 110. In the analysis of stroke this patient enters the analysis with day 100; in an analysis of fatal stroke this patient should also be included with day 100. However in an analysis of CV death the relevant day is day 110.

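### General AE and SAE tables are planned only as crude percentages in an on-treatment window; first-event rates per patient-year should stand beside them

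*SAP*

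**What the plan says.** SAP 7.8.1 describes the AE analysis as descriptive. The counting unit is the patient: "All analyses of AEs will be based on the number of patients with AEs and NOT on the number of AEs". The summary measure is the percentage: "Frequencies [N (%)] of patients with adverse events will be summarised by treatment, primary system organ class and preferred term (using MedDRA"), with separate tables for serious events. SAP 7 defines such a percentage as "percentage (%) relative to the respective treatment group", that is, all patients of the analysis set in that arm unless stated otherwise.

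The window is on treatment: "all adverse events occurring between first drug intake until 6 days after last drug intake will be assigned to the randomized treatment". Of later events, the SAP says that "all adverse events occurring after last drug intake + 6 days will be assigned to" the post-treatment category, which is in general only listed.

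The tables are meant for comparison. Protocol 7.3.3 says: "Standard BI summary tables and listings will be produced to compare the incidence of adverse events". SAP 7.7 adds that "Extent of exposure to trial medication within the study will be displayed by treatment", but neither document uses that exposure as a denominator for AEs. For further detail on AE summaries, SAP 7.8.1 points to a company guideline (reference 5), which is not among the documents.

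**The concern.** A percentage of patients with at least one event rises with the time during which events can be counted. Here that time ends 6 days after last intake, so it depends on how long each arm stays on drug. Suppose one arm stops permanently sooner. It then has less time in which to record an AE, and its percentages fall although its risk per unit of time is the same.

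Unequal stopping is foreseeable. The protocol associates dyspepsia-like effects with dabigatran (4.1.4), names bleeding as its most commonly reported adverse reaction (2.3), and lets AEs and bleeds lead to discontinuation (3.3.4.1, 4.2.1). A patient who stops because of an AE is still counted for that AE. What drops out of the table is any later, different AE beyond the 6 days.

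Characterising the safety of dabigatran is a stated objective (Protocol 2.2). For AEs without an endpoint analysis of their own, these tables are the only planned comparison in the visible text.

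**Working it through.** **Inputs from the documents.** N (%) of patients and the window (SAP 7.8.1); whole-arm denominator (SAP 7); 30 months of recruitment in a trial of about 36 months and 21 months average participation (Protocol 3.1, 3.3); "a Treatment Period of approximately 6-36 months" (Protocol 6.1); the declining stroke rates of Protocol Table 7.6:1. No AE rate and no stop rate by arm is given.

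**Assumptions.** All AE rates and stop rates below. The true AE risk is the same in both arms throughout, so an unbiased ratio is 1.

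**Check of the plan's own figure.** Uniform entry with follow-up from 6 to 36 months has mean (6 + 36)/2 = 21 months, as Protocol 3.1 states.

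**Step 1: fixed exposure.** With a constant rate of 0.05 per year, the percentage with an event is 1 − exp(−0.05 × years on drug).

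- 1.5 years: 1 − exp(−0.075) = 7.2%.
- 5% shorter, 1.425 years: 6.9%, ratio 0.95.
- 10% shorter, 1.35 years: 1 − exp(−0.0675) = 6.5%, ratio 0.90.
- 20% shorter, 1.2 years: 5.8%, ratio 0.81.

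**Step 2: staggered entry and random stopping.** Let AE rate = λ, stop rate = δ, s = λ + δ, and follow-up be uniform on 0.5 to 3 years. Stopping is unrelated to AE risk and the extra 6 days are ignored. Then

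crude % = (λ/s) × {1 − [exp(−0.5s) − exp(−3s)]/(2.5s)}.

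With λ = 0.05 and δ = 0.10: (0.05/0.15) × {1 − (0.9277 − 0.6376)/0.375} = 7.55%. This is the reference arm.

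| Stop rate in other arm | Mean months on drug (reference 19.0) | Crude % | Crude ratio | Patient-year rate ratio |
|---|---|---|---|---|
| 10%/yr | 19.0 | 7.55 | 1.000 | 1.000 |
| 15%/yr | 18.1 | 7.20 | 0.954 | 1.000 |
| 20%/yr | 17.3 | 6.88 | 0.911 | 1.000 |
| 30%/yr | 15.8 | 6.29 | 0.834 | 1.000 |

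**Step 3: rates when the hazard is not constant.** Same set-up by numerical integration, with the reference arm stopping at 10%/yr.

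| AE hazard | Stop rate in other arm | Crude ratio | Patient-year rate ratio |
|---|---|---|---|
| 7.4%, 3.2%, then 2.5%/yr (shape of Table 7.6:1) | 15%/yr | 0.967 | 1.014 |
| same | 20%/yr | 0.935 | 1.027 |
| same | 30%/yr | 0.878 | 1.054 |
| 60%/yr for 3 months, then 2%/yr | 20%/yr | 0.975 | 1.070 |
| same | 30%/yr | 0.952 | 1.142 |

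Table 7.6:1 describes stroke and is only a proxy for the shape of an AE hazard. With a declining hazard the rates err in the opposite direction. For an AE concentrated in the first 3 months, their error (7% and 14%) exceeds that of the crude percentage (2.5% and 5%).

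**The case against.** Several points on the other side stand.

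- **The imbalance is not shown.** No stop rate by arm is given, and with equal stopping both measures return 1. A reader might infer from the 6 to 36 month treatment period that the arms will differ in exposure. That range comes from staggered entry, which randomisation balances. The stopping rules for AF and low creatinine clearance are written for both blinded arms.
- **The scope is narrow.** A reader might infer that the whole safety comparison rests on crude percentages. It does not. The bleeding endpoints are time-to-event analyses by Cox model, with a randomized-set sensitivity analysis (Protocol 7.3.3, SAP 7.8). All-cause death, ischemic and disabling stroke, and the composite of nonfatal stroke, nonfatal MI and cardiovascular death are Cox-analysed in the randomized set over full follow-up (SAP 7.5). The AE tables are descriptive and carry no test.
- **The omission may be only apparent.** The guideline cited in SAP 7.8.1 and the standard company tables mentioned in Protocol 7.3.3 are not supplied and may already contain exposure-adjusted rates. Some text on further safety endpoints is not visible either.
- **Patient-year rates are not a cure.** It is tempting to say that they remove the bias and should replace the percentages. Step 3 shows otherwise: they are exact only with a constant hazard and stopping unrelated to AE risk.
- **Counting patients is not the fault.** A first-event rate counts the same patients. The issue is the percentage taken together with the window.

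One argument carries less weight. SAP 7.7 would let a reader see an exposure imbalance, but not how far it moves any particular AE percentage.

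**Conclusion.** The point holds as a modest gap in reporting. In the visible text, general AEs and SAEs are compared only as crude percentages of treated patients in a window that closes 6 days after last intake. If one arm leaves drug sooner, its percentages tend to understate its risk relative to the other arm. The ratio is about 0.95 to 0.81 for exposure 5% to 20% shorter, given a constant 5 per 100 patient-years, 18 months on drug in the longer arm, and a true ratio of 1. These are all assumptions; the direction follows from the design, but the size and even the presence of an effect depend on stop rates that the documents do not give. The documents do not support a claim that the planned tables are biased as they stand, or that rates alone would be right. The improvement is inexpensive and worth making.

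**What to change.** In SAP 7.8.1, keep N (%) and add to the AE and SAE tables the first-event rate per 100 patient-years at risk. Use the on-treatment time already defined in SAP 6.8: from first intake to first event or, without an event, to the earlier of last intake plus 6 days and last contact. If the cited guideline already requires this, one sentence saying so is enough.

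Show both measures side by side and do not rest between-arm statements on the rates alone. Add a note that the rates assume a roughly constant hazard and non-informative stopping, and can over-correct for early-onset AEs. Say also that this time includes temporary interruptions, which Protocol 4.2 permits.

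No new data are needed. The cost is some programming: each preferred term needs its own time at risk, so the total exposure of SAP 7.7 cannot simply be reused.

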7.8.2 Laboratory data

The analyses of laboratory data will be descriptive in nature and will be based on BI standards [\[6\]](#).

7.8.3 Vital signs

Only descriptive statistics are planned for this section of the report.

7.8.4 ECG

ECGs will be evaluated centrally by an external vendor. Summary statistics will be displayed at baseline. Additional summaries will be produced for patients who have abnormal ECG findings at baseline or during the study period.

7.8.5 Others

Duration of cardiac monitoring performed during the course of the trial and the observed duration of atrial fibrillation (from this monitoring) will be summarized using descriptive statistics.

10. HISTORY TABLE

This is a revised TSAP including the following modifications to the final TSAP.

Table 10: 1 History table

Version	Date (DD-MMM-YY)	Author	Sections changed	Brief description of change
Final	29-JUL-14		None	This is the final TSAP without any modification.
Revised	14-NOV-14		6.2, 6.3,	Table 6.2: 1 (Important PVs) inserted.
Revised	11-AUG-15		4, 6.2, 6.3, 7.8.5 6.6,	Section 6.6 missing data rules added for NIHSS. Other changes due to Amendment 1 are summarized in Section 4.
Revised	10-APR-18		2, 4, 5.1, 6.1, 6.2, 6.3, 6.6, 6.7, 6.8, 7.3, 7.4, 7.5.1, 7.7, 7.8, 7.8.4	Section 6.8 added to specify time to event calculation rules. Rule to define full follow-up added to Section 6.7. Additional changes in 5.1, 6.1, 6.3, 7.3, 7.5.1, 7.7, 7.8 are wording clarifications.
